## Listing of Creatine Kinase and Adverse Events Linked with [\* (See below)].

Disease Status: Metastatic									
Center/ Patient ID	Lab Data				AE Data				
	Visit of CK Sample	Date of Lab Sample (day)	CK Value (U/L)	CTC Grade	Reported term of AE	Date of AE Start (day)	Date of AE End (day)	CTC Grade	
xxxxxx/xxx	CxxDx	xxxx-xx-xx (xxx)	xx	x	CREATININE SERUM HIGH	xxxx-xx-xx (xxx)	Ongoing	x	
	FU xx DAYS	xxxx-xx-xx (xxx)	xx	x	CREATININE SERUM HIGH	xxxx-xx-xx (xxx)	Ongoing	x	
	FU x MONTHS	xxxx-xx-xx (xxx)	xx	x	CREATININE SERUM HIGH	xxxx-xx-xx (xxx)	Ongoing	x	
xxxxxx/xxx	FU xx DAYS	xxxx-xx-xx (xxx)	xx	x	CREATININE SERUM HIGH	xxxx-xx-xx (xxx)	xxxx-xx-xx (xxx)	x	
xxxxxx/xxx	FU x MONTHS	xxxx-xx-xx (xxx)	xx.x	x					
xxxxxx/xxx	FU x MONTHS	xxxx-xx-xx (xxx)	xxx	x					
xxxxxx/xxx	CxDx	xxxx-xx-xx (xx)	xx	x					
	CxDx	xxxx-xx-xx (xx)	xx	x					
	END OF STUDY	xxxx-xx-xx (xxx)	xx	x					
	FU xx DAYS	xxxx-xx-xx (xxx)	xx	x					
	FU xx DAYS	xxxx-xx-xx (xxx)	xx	x					
	FU xx DAYS	xxxx-xx-xx (xxx)	xx	x					

Investigator text for AEs encoded using MedDRA version xx.x.  
Listing shows Windowed Visits.  
PRE-BASELINE Visits can include Screening or other visits collected prior to Dosing.  
For some patients, Screening and Baseline visits were done on the same day and results were duplicated.

### Programming Notes:

- Safety-Evaluable patients are included in the listing.
- \* would be Creatine Kinase and Adverse Events of Linked to AE with Muscle Spasms, Elevated Creatinine, Renal Insufficiency, Elevant Transaminase (ALT or AST). (ie, Listing of Creatine Kinase and Adverse Events Linked with Muscle Spasms).
- Create a separate listing for Creatine Kinase and Adverse Events of Linked to AE with Muscle Spasms, Elevated Creatinine, Renal Insufficiency, Elevant Transaminase (ALT or AST).
- Where possible, merge Lab Creatine Kinase Samples Dates with AE Start Date of XXX AE and display on same line.
- Display all the records of lab Creatine Kinase which include Visit, Sample Date(with study Day), CPK Standard Result and CTC Grade. For Adverse Events include Reported Term, Start and End Date and CTC Grade.

Listing of Lab Data:

STREAM Template	Description
N/A	Output ID: I_lb_* 
 
● Analysis Population: Safety Evaluable
 
● Column Variables: Center, Patient ID, Windowed Visit, relevant Lab test (within Lab Category) and results in SI Units.
 

Programming Note:

- Create Table for Lab Categories: Hematology and Biochemistry. Also repeat for all tests within Hematology and Biochemistry with a Shift from Grades 3 to 4.

Listing of Hormone Results for Subjects with Amenorrhea or Irregular Menses:

A subject is considered to have Amenorrhea or Irregular Menses if they have a record of either according to the AE CRF page.

STREAM Template	Description
N/A	Output ID: I_lb_hrm_* 
 
● Analysis Population: Safety Evaluable
 
● Column Variables: Center, Patient ID, Parameter with SI Unit, Windowed Visit, Date of Sample Collection, Result in SI Units and High / Low Range indicator
 

## Listing of Serum Pregnancy Results for Subjects with Amenorrhea or Irregular Menses:

A subject is considered to have Amenorrhea or Irregular Menses if they have a record of either according the the AE CRF page.

STREAM Template	Description
N/A	Output ID: I_lb_preg_* 
 
● Analysis Population: Safety Evaluable
 
● Column Variables: Center, Patient ID, Windowed Visit, Date of Sample Collection, Character Result and Specimen Type
 

## Listing of Ultrasound Results for Subjects with Amenorrhea or Irregular Menses:

A subject is considered to have Amenorrhea or Irregular Menses if they have a record of either according the the AE CRF page.

STREAM Template	Description
N/A	Output ID: I_lb_ult_* 
 
● Analysis Population: Safety Evaluable
 
● Column Variables: Center, Patient ID, Windowed Visit, Date of Examination, Character Result, Abnormality Specified, Is Abnormality Significant? and Method of Test or Examination
 

ECG:

## Statistical Summary of Electrocardiogram

DMT01	
Output ID: t_eg_*
 

● Analysis Population: Safety-Evaluable Patients

● Column Variables: Disease status (Locally Advanced, Metastatic)

● Column Totals: Total of non-missing Disease status

● Analysis Variables: Number of Patients in each Visit with ECG results Number of Patients with ECG Normal Result in each Visit Number of Patients with Abnormal, not clinically relevant in each Visit Number of Patients with Abnormal, not clinically relevant in each Visit

● Numeric Precision and Formatting of Statistics: Use standard display in the mockup

--------------	--

Programming Note:

- Summary will be displayed by Visit.
- Baseline is the patient's last observation prior to initiation of study drug.
- If multiple records were collected during the same cycle, then the worst record within that cycle is used for the analysis.

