5.3.3 End of Treatment Visit Assessments

The End of Treatment Visit will be performed when the patient discontinues vismodegib, regardless of when it occurs.

The following evaluations will be conducted at the End of Treatment Visit:

- Limited physical examination
- Vital signs (body temperature, blood pressure, and pulse) and weight
- ECOG PS assessment

- Hematology (including hemoglobin, hematocrit, red blood cell count, full white blood cell count including differential, platelet count, and ANC)
- Biochemistry (including glucose, sodium, potassium, chloride, bicarbonate, blood urea nitrogen, creatinine, creatine kinase [also known as creatine phosphokinase], total bilirubin, alkaline phosphatase, AST, and ALT)
- Tumor assessment
- 12-lead ECG (if clinically indicated)
- Concomitant therapy and new anti-cancer therapy
- AEs (including SAEs)
- For women of childbearing potential:
 - Record date of last menses
 - Assess amenorrhea/irregular menses that develops while on study:
 1. At start of amenorrhea/irregular menses, perform serum hormone evaluation at study site, including FSH, LH, E2, and TSH, and refer to gynecologist or appropriate specialist for assessment of ovaries and uterus, including ultrasound
 2. At resolution of amenorrhea/irregular menses, perform serum hormone evaluation at site, including FSH, LH, E2, and TSH. Refer to gynecologist or appropriate specialist for follow-up ultrasound ONLY if there was abnormality identified during previous ultrasound
 3. If amenorrhea/irregular menses recurs, repeat evaluations at start of recurrence as detailed previously
- Follow up for disease progression
- Pregnancy test for women of childbearing potential
- In selected sites, patients will complete the Skindex-16 Quality of Life questionnaire (see Section 5.5 and Appendix 5).
- Patients with metastatic BCC (newly enrolled after approval of the Study Protocol, version 4.0) will complete the M.D. Anderson Symptom Inventory (see Section 5.6 and Appendix 6), prior to having any other assessments performed
- In metastatic BCC patients who develop tumor progression on vismodegib treatment, a biopsy will be performed if at least one of the progressing lesions is accessible, e.g., skin, superficial mass, or lymph node
- Collection of whole blood in metastatic BCC patients with tumor biopsy at progression

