5.3.12 Electrocardiographic Assessment

Electrical activity of the heart will be assessed by standard twelve-lead electrocardiograms (ECGs). ECGs will be performed at screening and thereafter throughout the study and at the End of Treatment Visit, as clinically indicated.

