## Listing of Electrocardiogram

ECG data will be listed. Displayed columns will be: Subject ID; Disease Status; Age; Sex; Race; Windowed Visit; Date of ECG; ECG Status; ECG Result.

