## Vitals:

### Statistical Summary of Vital Signs, Population

VST01	
Output ID: t_vs_*
 

● Analysis Population: Safety-Evaluable Patients

● Column Variables: Disease Status (Locally Advanced, Metastatic)

● Column Totals: Totals of non-missing Disease Status

● Analysis Variables: Following parameters are to be summarized.

○ Diastolic Blood Pressure

○ Systolic Blood Pressure

○ Heart Rate

○ Temperature

○ Weight

● Statistics and Calculation Methods: Use proc means or proc univariate.

○ n, mean (SD), median, 25th-75th Percentiles and min-max statistics are to be included in the table.

○ N in the column heading is the number of patients in a disease status in the analysis population. n in the rows is the number of patients with available data at the visit.

○ Change from baseline at Visit X is defined as (Visit X value – baseline value). Only patients with non-missing values at both baseline and Visit X are included in calculating change from baseline at Visit X.

○ All Visit after Windowing would be displayed in this table. With repeat Vital sign measurements in a same Visit, the last non-missing value is reported.

○ Vital sign measurements collected 30 days after the last dose of study drug should be excluded from summaries of actual values and changes from baseline.

● Numeric Precision and Formatting of Statistics: Level of precision for means, SDs, and medians is one digit more than the level of precision

--------------	--

	of the vital sign measurement (e.g. pulse reported to a single place after the decimal point). Present the minimum and maximum to the level of precision of the measurement.
--	--

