### Programming Note:

- N is Number of Patients in each Disease Status.
- Shift of ECOG Grade for each Visit from Baseline will be summarised.
- Percentages will be calculated based on N in each Disease status.
- If multiple records were collected during the same cycle, then the last record within that cycle is used for the analysis.
- Population : Intent to treat Population

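### The by-visit ECG summary has no row for clinically relevant abnormalities, and the by-visit ECOG shift percentages shrink with the share of the cohort assessed

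*SAP*

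**What the plan says.** **ECG.** The SAP section Statistical Summary of Electrocardiogram specifies four rows per visit. The first is "Number of Patients in each Visit with ECG results" and the second is the number with a normal result. The last two are "Number of Patients with Abnormal, not clinically relevant in each Visit Number of Patients with Abnormal, not clinically relevant in each Visit". Where a cycle holds several records, "the worst record within that cycle is used for the analysis". The next section, Listing of Electrocardiogram, prints for each patient, among other columns, "Windowed Visit; Date of ECG; ECG Status; ECG Result". Protocol 5.3.12 has ECGs at screening and "thereafter throughout the study and at the End of Treatment Visit, as clinically indicated".

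**ECOG.** The shift table from baseline is produced for each visit, separately for locally advanced and metastatic disease. Its programming note defines N as the patients in the disease-status group and adds: "Percentages will be calculated based on N in each Disease status". The mock-up holds placeholders only. It has cell counts, a Missing row and column, and a Total row and column.

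**Elsewhere in the SAP.** In the vital signs summary, "n in the rows is the number of patients with available data at the visit"; the Skindex-16 tables do the same. The MDASI reduction table bases percentages on the small n. The table of CPK elevations by maximum grade prints two percentages, one of all patients and one of patients with a value.

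Protocol 8.1.2 names both ECG and ECOG performance status as secondary safety variables. Protocol 8.2 plans no hypothesis tests.

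**The concern.** These are operative output specifications, so a programmer who follows them literally will produce what they describe.

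For ECG, the category that matters most clinically would be absent from the only tabular summary of ECG results in the SAP as supplied. The worst-record rule makes the gap more visible: when a patient's worst ECG in a cycle is a clinically relevant abnormality, the rule selects that record and the table then has nowhere to put it.

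For ECOG, the denominator stays fixed while the number of patients contributing falls. Patients leave through progression, toxicity, withdrawal or death. The SAP also applies a data cut, so patients who had not yet reached a late visit remain in the denominator too. A percentage with worsened status can then fall from one visit to the next with no change in anyone's condition. Protocol 8.2.2 promises the percentage of patients in each ECOG category at different time points, and a reader would naturally take that as describing the patients seen at the time point.

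**Working it through.** **Step 1. ECG rows.** Take a patient with a normal ECG and a clinically relevant abnormal ECG in the same cycle. The worst-record rule keeps the second. The patient is counted among those with results, but not as normal and not as abnormal without clinical relevance. The missing category at a visit would be

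(patients with results) − (normal) − (abnormal, not clinically relevant),

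which is valid only if these are the only result categories. The ECG case report form is not shown, so that is an assumption. The table states no denominator for its percentages.

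**Step 2. Check the denominator effect on SAP tables that carry figures.**

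- CPK elevations, any time after version 4 consent: 204/677 = 30.1% of all patients and 204/514 = 39.7% of patients with a value. Both match the mock-up. The share with a value is 514/677 = 75.9%, and 0.759 × 39.7% = 30.1%. The full-cohort figure is lower by 1 − 0.759 = 24% in relative terms.
- Alkaline phosphatase shift, locally advanced: 787/1119 = 70.3% and 1079/1119 = 96.4%, again as printed. Worsened patients number 138 + 20 + 5 + 12 + 2 = 177, which is 177/1119 = 15.8% of the cohort and 177/1079 = 16.4% of those with both grades. The choice hardly matters here, because 96.4% of the cohort contributes.

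**Step 3. Apply this to the ECOG shift.** For any cell,

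printed % = (share of cohort assessed at the visit) × (% among those assessed).

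The share by visit is not in the documents, so it is varied. Assume that 20% of those assessed have worsened, with N = 1119 as in the locally advanced mock-ups:

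| Share assessed | Assessed | Worsened | Printed % (of 1119) | % of assessed |
|---|---|---|---|---|
| 100% | 1119 | 224 | 20.0 | 20.0 |
| 90% | 1007 | 201 | 18.0 | 20.0 |
| 75% | 839 | 168 | 15.0 | 20.0 |
| 50% | 560 | 112 | 10.0 | 20.0 |
| 25% | 280 | 56 | 5.0 | 20.0 |

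In the metastatic group (N = 96) with half assessed, 10 worsened of 48 is 20.8%, printed as 10/96 = 10.4%.

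**Step 4. Direction.** Improvement is scaled by the same factor. If 10% of the 560 assessed have improved, that is 56 patients: 56/560 = 10.0%, printed as 56/1119 = 5.0%. The ratio of worsened to improved is 112:56 under either denominator.

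**Step 5. Limits of an assessed-only percentage.** With 560 assessed and 112 worsened, 559 patients are unobserved. The share of the whole cohort that has worsened could lie anywhere from 112/1119 = 10.0% (none of the 559) to (112 + 559)/1119 = 60.0% (all of them). The 20% among those assessed is one value inside that range, so the number not assessed has to be shown beside it.

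**The case against.** The case against has several sound parts.

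- The repeated ECG label follows a row for results, a row for normal and a row for abnormal without clinical relevance, so the intended fourth row is obvious. This is almost certainly a copying error. The worst-record rule works against hiding harm, the number with results is printed, and the listing shows every status and result. All of this stands. The specification still has to be corrected, because readers should not need a listing or a subtraction to find this category.
- The ECOG mock-up prints counts and Missing and Total cells, so a reader can probably re-base a percentage. This stands in part. The placeholders do not show whether the Missing row holds patients who have left or not yet reached the visit, and the programming note does not say.
- Full N is also used in the laboratory shift tables. That is so, but those take one worst grade over the treatment period, and in the parameter shown 96.4% contribute. The ECOG table is repeated at every visit.
- Restricting to assessed patients has its own bias, since those who progressed or died drop out. This stands and shapes the fix.

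A reader might infer that both tables understate harm. The documents do not support that. No printed ECG rate is lowered, and the ECOG rule shrinks improvement as much as worsening and leaves the counts intact.

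A reader might also try to size the dilution from the 9.7-month median treatment duration of the locally advanced cohort in the earlier phase II trial (Protocol 1.1.2.2). That is another study, its observed range ended at 18.7 months, and nothing supports a particular shape for the duration curve.

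**Conclusion.** Two separate specification defects hold.

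- **ECG:** as written, the by-visit summary omits clinically relevant abnormalities. They remain in the listing, and can be had by subtraction if the result categories are only the three assumed. The effect is an omitted category, not a biased rate.
- **ECOG:** all shift percentages are diluted in proportion to the share of the cohort assessed at the visit. An assumed 20% worsening among those assessed prints as 10% with half assessed and 5% with a quarter. These are illustrations, because the actual shares are not in the documents.

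Both outputs are descriptive and concern secondary safety variables, so no test or primary conclusion is affected. The corrections are nearly free and make the tables show what they are meant to show.

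**What to change.** **ECG table.**

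- Change the second abnormal label to 'Abnormal, clinically relevant'.
- Base percentages on patients with an ECG at that visit.
- Add a footnote that treatment-phase ECGs are done only when clinically indicated, so those patients are a selected group.
- If a patient-level row for any clinically relevant abnormality after baseline is added, give it as a count with the same caveat.

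**ECOG shift table.**

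- Base percentages on patients with a grade at both baseline and that visit and show that n, or print both denominators as the CPK table does.
- Report patients not assessed as a count, including deaths and discontinuations, because the assessed-only percentage can miss deterioration among those who left.
- State what the Missing row contains.

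**Separate point.** Protocol Table 1 marks the End of Treatment ECG without a condition, while Sections 5.3.3 and 5.3.12 make it conditional on clinical indication. These passages must be reconciled, because they decide whether any post-baseline ECG is unselected.

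**Cost.** SAP wording and minor code, with no new data. Later-visit ECOG percentages, worsened and improved alike, will print higher than under the present rule.

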## Listing of Electrocardiogram

ECG data will be listed. Displayed columns will be: Subject ID; Disease Status; Age; Sex; Race; Windowed Visit; Date of ECG; ECG Status; ECG Result.

## Vitals:

### Statistical Summary of Vital Signs, Population

VST01	
Output ID: t_vs_*
 

● Analysis Population: Safety-Evaluable Patients

● Column Variables: Disease Status (Locally Advanced, Metastatic)

● Column Totals: Totals of non-missing Disease Status

● Analysis Variables: Following parameters are to be summarized.

○ Diastolic Blood Pressure

○ Systolic Blood Pressure

○ Heart Rate

○ Temperature

○ Weight

● Statistics and Calculation Methods: Use proc means or proc univariate.

○ n, mean (SD), median, 25th-75th Percentiles and min-max statistics are to be included in the table.

○ N in the column heading is the number of patients in a disease status in the analysis population. n in the rows is the number of patients with available data at the visit.

○ Change from baseline at Visit X is defined as (Visit X value – baseline value). Only patients with non-missing values at both baseline and Visit X are included in calculating change from baseline at Visit X.

○ All Visit after Windowing would be displayed in this table. With repeat Vital sign measurements in a same Visit, the last non-missing value is reported.

○ Vital sign measurements collected 30 days after the last dose of study drug should be excluded from summaries of actual values and changes from baseline.

● Numeric Precision and Formatting of Statistics: Level of precision for means, SDs, and medians is one digit more than the level of precision

--------------	--

	of the vital sign measurement (e.g. pulse reported to a single place after the decimal point). Present the minimum and maximum to the level of precision of the measurement.
--	--

## **Output Specifications: Questionnaires**

### **ECOG:**

Patients will be graded according to the Eastern Cooperative Oncology Group performance status scale and criteria as described below at each scheduled Visit mentioned in the Protocol:

Grade	ECOG
0	Fully active, able to carry on all pre-disease performance without restriction
1	Restricted in physically strenuous activity but ambulatory and able to carry out work of a light or sedentary nature, e.g., light housework, office work
2	Ambulatory and capable of all self-care but unable to carry out any work activities.
3	Capable of only limited self-care, confined to bed or chair more than 50% of waking hours
4	Completely disabled. Cannot carry on any self-care. Totally confined to bed or chair
5	Dead

## Shift Table from Baseline: Eastern Cooperative Oncology Group Performance Score

Visit: C1D1								
Status at Baseline								
	Grade 0	Grade 1	Grade 2	Grade 3	Grade 4	Grade 5	Missing	Total
Locally Advanced (N=xxxx)								
Grade 0	x ( x.x%)		x	x	x	x	x	x ( x.x%)
Grade 1	x ( x.x%)	x ( x.x%)	x	x	x	x	x	x ( x.x%)
Grade 2	x	x (<x.x%)	x	x	x	x	x	x (<x.x%)
Grade 3	x	x	x	x	x	x	x (<x.x%)	x (<x.x%)
Grade 4	x	x	x	x	x	x	x	x
Grade 5	x	x	x	x	x	x	x	x
Missing	x	x	x	x	x	x	x	x
Total	x ( x.x%)	x ( x.x%)	x	x	x	x	x (<x.x%)	xx ( x.x%)
Metastatic (N=xxxx)								
Grade x	x ( x.x%)	x	x	x	x	x	x	x ( x.x%)
Grade x	x	x	x	x	x	x	x	x
Grade x	x	x	x	x	x	x	x	x
Grade x	x	x	x	x	x	x	x	x
Grade x	x	x	x	x	x	x	x	x
Grade x	x	x	x	x	x	x	x	x
Missing	x	x	x	x	x	x	x	x
Total	x ( x.x%)	x	x	x	x	x	x	x ( x.x%)

### Programming Note:

- N is Number of Patients in each Disease Status.
- Shift of ECOG Grade for each Visit from Baseline will be summarised.
- Percentages will be calculated based on N in each Disease status.
- If multiple records were collected during the same cycle, then the last record within that cycle is used for the analysis.
- Population : Intent to treat Population

## Skindex-16 QoL Questionnaire:

Skindex-16 (Appendix 1) is a 16-question instrument that has been validated to accurately measure the extent patients are bothered by certain skin conditions. Each question asks the degree to which a patient has been concerned by their specific skin condition in the week prior to administration of the questionnaire. Patients answer every question with a number ranging from 0 (“never bothered”) to 6 (“always bothered”). In terms of scoring algorithm, responses to each item are transformed to a linear scale of 100, varying from 0 (“never bothered”) to 100 (“always bothered”). Thus, each item has a minimum score of 0 and a maximum score of 100. With the exception of the 16 individual scores, three domain scores (symptom [items 1 – 4], emotion [items 5 – 11], and function [items 12 – 16]) are grouped and calculated as their means ranging from 0 to 100).

Below Table summarizes the Skindex-16 scoring algorithm.

Table: Skindex-16 Scoring Algorithm

Question	Response Option and Score Algorithm 
During the past week, how often have you been bothered by:	
If Q(i) = “never bothered,” then single item original score Q(i)=0
 
if Q(i)=”always bothered,” then single item original score Q(i) = 6

Question 1 - 4: 1) Itching, 2) Burning/stinging 3) Hurting 4) Being irritated	
Individual Skindex-16 Q1 to Q4 = (original item score)*100/6
 
Symptom Domain Score = [(sum of original item scores of Q1 to Q4)*100/6]/4

Question 5 - 11: 5) Persistence/reoccurrence 6) Worry 7) Appearance 8) Frustration 9) Embarrassment	
Individual Skindex-16 Q5 to Q11 = (original item score)*100/6
 
Emotion Domain Score = [(sum of original item scores of Q5 to

10) Being annoyed 11) Feeling depressed	$Q11) * 100 / 6] / 7$
Question 12 - 16: 12) Interaction with others, 13) Desire to be with people, 14) Show affection 15) Daily activities 16) Work or do what you enjoy	Individual Skindex-16 Q12 to Q16 = $(\text{original item score}) * 100 / 6$ Function Domain Score = $[(\text{sum of original item scores of Q12 to Q16}) * 100 / 6] / 5$

Note: Q = question item

 The “50% missing rule” which is commonly cited and used in patient-reported outcome analysis is used. If more than 2 items for the symptom domain, more than 4 items for the emotion domain, or more than 3 items for the function domain are missing, their respective domain values should be regarded as missing. Otherwise, the sum of the nonmissing item scores should be calculated as the domain score by using the formula stated in the table and denominator should be total no. item with non-missing score.

